Pilot Mobile for Dementia and Frailty (Mindful Meals)

NCT05827094

April 23, 2023

STUDY PROTOCOL

Objective

We conducted a pilot randomized controlled trial (RCT) to assess the feasibility and preliminary efficacy of an innovative, theory-driven mobile intervention specifically designed for older adults with frailty and dementia, aimed at increasing Mediterranean food consumption. Primary efficacy outcome was adherence to the Mediterranean diet score.

Design

This was a pilot randomized control trial (RCT) to test the feasibility and preliminary efficacy of a mobile intervention consisting of a patient-facing mobile app and a secure web-based administrative dashboard. Participants were randomly assigned to either the intervention group or the control group. Those randomized to the intervention received access to a mobile app, available for download by invitation only on the Apple App Store. Participants randomized to control received via email referral to National Institute on Aging (NIA) materials concerning healthy eating.

Methods

Participants

Eligibility criteria included: a) being age 65 years and older, b) having difficulty with at least one of the following activities: performing heavy housework; performing light housework; walking outside alone; managing money/paying bills; shopping for personal items; preparing meals, suggestive of frailty, 3) being diagnosed with early dementia or having memory symptoms suggestive of mild cognitive impairment. Exclusion criteria included: a) having difficulty with basic activities of daily living such as eating and getting

out of bed, suggestive of overt disability, b) having a 14-item Mediterranean Diet Adherence Screener (MEDAS) >8, suggestive of an optimal diet, d) severe hearing or visual impairment.

STATISTICAL ANALYSIS PLAN

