Descriptive statistics were first calculated to compare demographic characteristics between the intervention and the control groups. Outcomes measures were analyzed by calculating the within-group pretest–post-test change scores and then comparing the change scores between the intervention and the control groups using Mann–Whitney U tests. To estimate the magnitude of the intervention's impact compared to the control group, we used Hedges' g to measure effect size. Hedges' g is a variation of Cohen's d that corrects for biases that may occur in small sample sizes, making it a more appropriate choice for our study. Hedges' g takes the difference in means between the intervention and control groups and divides it by the pooled standard deviation while applying a correction factor to account for potential biases. A larger absolute value of Hedges' g indicates a greater effect size, with values of 0.2, 0.5, and 0.8 generally considered small, medium, and large effect sizes, respectively. An R package, "BootES" was used to calculate 95% bootstrap confidence intervals for the effect sizes. The "BootES" package is designed specifically for this purpose, providing a robust and efficient method for estimating confidence intervals based on resampling techniques. Finally, descriptive statistics and visual analytics were used to describe app quality and to analyze log data of user interactions.

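### Does the feasibility aim need a defined measure, denominator and confidence interval added to the analysis plan?

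*Combined protocol and SAP*

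**What the plan says.** The Objective says the trial was run "to assess the feasibility and preliminary efficacy of an innovative, theory-driven mobile intervention", and the Design section repeats that it was a pilot "to test the feasibility and preliminary efficacy of a mobile intervention". The one outcome named is on the efficacy side: "Primary efficacy outcome was adherence to the Mediterranean diet score". Under Design, the intervention arm "received access to a mobile app, available for download by invitation only on the Apple App Store", while the control arm was emailed a referral to healthy-eating materials.

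The Statistical Analysis Plan opens with a descriptive comparison of the arms' demographics. It continues "Outcomes measures were analyzed by calculating the within-group" change from pretest to post-test, and compares those changes between arms by Mann–Whitney U tests. Hedges' g is the effect size, and an R bootstrap package "was used to calculate 95% bootstrap confidence intervals for the effect sizes". The section ends by stating that "descriptive statistics and visual analytics were used to describe app quality and to analyze log data of user interactions".

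Neither part gives a sample size, a definition of feasibility, a success criterion, or a denominator for app use.

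**The concern.** Of two stated aims, efficacy has a named outcome, a test, an effect size and an interval, while feasibility has none of these. The method given for outcome measures cannot supply a feasibility estimate. Completion and app use have no pretest value from which to compute a change, and only one arm is described as receiving the app.

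The denominator could matter here. Participants had early dementia or memory symptoms, and the app had to be downloaded by invitation, so being assigned to the app and using it are separate events. A usage summary restricted to people who opened the app would look better than one over everyone assigned to it. Use among all those assigned also helps in reading the effect size: the same Hedges' g could come from a strong app that few opened or a weak one that most used. At pilot size, a bare percentage also conceals a wide range.

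**Working it through.** **1. Is there a plan figure to reproduce?** No. The documents give no sample size, allocation ratio, dropout rate or feasibility target. The concern is about an omission, so the texts have to be set side by side.

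**2. What does each candidate feasibility quantity need, and is its source already in the plan?**

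| Quantity | Numerator | Denominator | Source named in the documents |
|---|---|---|---|
| Post-test completion, by arm | people with a post-test score | people randomised to that arm | change-score analysis; random assignment |
| App use | people with logged interactions | people randomised to the app | log-data analysis; random assignment |
| App quality | ratings or other quality data | not stated | descriptive analysis of app quality |

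The first row comes almost free. A change score needs both a pretest and a post-test, so comparing changes between arms makes the analyst count how many people in each arm have both. The second row falls within the planned log analysis, since counts and percentages are ordinary descriptive statistics. Two things are not stated: whether app use is taken over everyone assigned to the app, and whether the logs can be linked to individual participants.

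**3. How imprecise would a bare percentage be?** Assume an observed 80% with 10 to 40 people in the denominator; neither figure comes from the documents. The exact (Clopper–Pearson) 95% limits for x out of n are

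- lower = the 2.5% quantile of Beta(x, n − x + 1)
- upper = the 97.5% quantile of Beta(x + 1, n − x)

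| x/n | Exact 95% interval | Wilson 95% interval |
|---|---|---|
| 8/10 | 44.4–97.5% | 49.0–94.3% |
| 16/20 | 56.3–94.3% | 58.4–91.9% |
| 24/30 | 61.4–92.3% | 62.7–90.5% |
| 32/40 | 64.4–90.9% | 65.2–89.5% |

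At 16/20 the exact interval spans 94.3 − 56.3 = 38 percentage points. The imprecision is real, but it depends only on x and n. Once both are reported, the interval follows from the formula above, so leaving it out of the plan loses no information.

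**4. Two further arguments that do not add weight.**

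- *The bootstrap fails for a proportion at its boundary.* With 20/20, resampling can only return 100–100%, whereas the exact interval is 83.2–100%. That is true, but the plan applies the bootstrap only to effect sizes and never proposes it for a proportion.
- *An uncertain completion rate would mislead a later trial.* Dividing 100 by 0.80 gives 125 randomised per 100 with a post-test, and the limits for 16/20 give 106.1 to 177.5. The documents mention no later trial. Planning a two-arm trial would also naturally pool completion over arms. With 20 per arm that is 32/40, giving 110.0 to 155.4, a narrower range than the single-arm figure.

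**The case for a change.** The strongest case for a change is that a description still needs a stated measure and denominator. The closing sentence of the Statistical Analysis Plan names topics, not measures, and does not tie them to feasibility. App logs cannot show post-test completion in a control arm that had no app. The authors thought intervals worthwhile for one aim, so leaving the other without them looks uneven. The remedy is cheap: a paragraph and a small table.

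Much of this stands as description. Feasibility is an aim without a named measure, retention is not mentioned, and the denominator for app use is open.

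It does not amount to a fault in the plan, for four reasons. First, it would be too strong to say that no estimate of uptake is planned, because an analysis of user interactions is planned; what is missing is its specification. Second, the thinness is not peculiar to feasibility. The efficacy side also lacks a post-test time point, an analysis population and a sample size, so the contrast between the two aims is smaller than it first appears. Third, nothing in the documents calls for an interval on a feasibility proportion, and the choice between exact and Wilson is a preference with little consequence (56.3–94.3% against 58.4–91.9% at 16/20). Fourth, the cost is less certain than it sounds, because ever-use among all those assigned depends on log linkage that the documents do not describe.

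**Conclusion.** No change to the plan follows. The omission is genuine, but it is a gap that analysts fill sensibly: completion by arm and app use, each as a count over those randomised, are what a pilot report would ordinarily contain. The documents do not show that such counts were not kept or reported. No stated figure, rule or analysis is wrong, and the change-score comparison, Hedges' g and its interval are unaffected.

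The size is illustrative only. For an assumed 80%, the exact interval is about 53 points wide at 10 (97.5 − 44.4) and about 27 points wide at 40 (90.9 − 64.4). These widths rest on an assumed proportion and assumed denominators; they say nothing about what happened in this trial. Because the text describes completed work, any definition of sustained use or success threshold written now would be post hoc, so amending the plan would not buy pre-specification. The conclusion assumes that the report gives numerators and denominators. A usage percentage published without its denominator would be a fault of that report.
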